### 8.2.2 Patient Eligibility

The following four new user cohorts based on available data in a claims database will be created: (1) erenumab-aooe, (2) other mAbs targeting the CGRP pathway, (3) selected SOC migraine preventive medications (anti-epileptics), and (4) onabotulinumtoxinA. The index date is defined as the date of first claim for each of these group of medications. Use of mAbs targeting the CGRP pathway based on free/discount/coupon programs is not captured in claims data, therefore in the current protocol the term "new users" for these medications refers to the first appearance of a claim for the medication in the claims database and not necessarily the first time the patient has used the medication. Because treatment guidelines recommend inadequate response or intolerance to two SOC migraine preventive medications prior to erenumab initiation, the SOC anti-epileptic preventive medication cohort and the botulinum toxin cohort will be selected from the remaining population of migraine patients after the erenumab and other CGRP mAbs cohorts have been created.

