#### 8.2.2.2 Exclusion Criteria

- (1) For the new user cohorts of mAbs targeting the CGRP pathway, no use of any medication targeting the CGRP pathway (erenumab-aooe, galcanezumab-gnlm, fremanezumab-vfrm, eptinezumab-jjmr, ubrogepant, rimegepant) in the year prior to the index date.
- (2) For the SOC migraine preventive medications (anti-epileptics) new user cohort, no use of any of the migraine preventive anti-epileptics: (topiramate, valproic acid, divalproex sodium), or any medication targeting the CGRP pathway in the year prior to the index date.
- (3) For the onabotulinumtoxinA new user cohort, no use of any onabotulinumtoxinA or any medication targeting the CGRP pathway in the year prior to the index date.

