### 8.2.5 Study Follow-up

Follow-up will be evaluated in two ways. With an 'intention-to-treat' analysis, patients will be followed for all available time after they initiate a medication, irrespective of whether they discontinue the medication or not, or whether they switch to an alternate medication or not. Follow-up begins the day after the index date and ends at first occurrence of: (a) the outcome of interest, (b) disenrollment from a health plan, or (c) end of study period.

With a 'per-protocol analysis' patients are followed for as long as they are actively taking the medication of interest during the follow-up period. Follow-up begins the day after the index date and ends at first occurrence of: (a) the outcome of interest, (b) disenrollment from the health plan, (c) discontinuation of study medication, (d) switching to the alternate medication, or (e) administrative end of study. When a gap greater than the allowable gap of 30 days is encountered, discontinuation of study medication occurs at the end of the last prescription which includes the days supply (+60 day extension). Censoring due to switching will occur for the new user cohorts in this study when the following conditions are met:

- (1) For new users of erenumab-aooe, initiation of any other medication targeting the CGRP pathway (galcanezumab-gnlm, fremanezumab-vfrm, eptinezumab-jjmr, ubrogepant, rimegepant) during the follow-up period.
- (2) For new users of other mAbs targeting the CGRP pathway, initiation of erenumab-aooe, ubrogepant, or rimegepant during the follow-up period.
- (3) For new users of the SOC migraine preventive medications (anti-epileptics), initiation of any medication targeting the CGRP pathway (erenumab-aooe, galcanezumab-gnlm, fremanezumab-vfrm, eptinezumab-jjmr, ubrogepant, rimegepant) during the follow-up period.
- (4) For new users of onabotulinumtoxinA, initiation of any medication targeting the CGRP pathway (erenumab-aooe, galcanezumab-gnlm, fremanezumab-vfrm, eptinezumab-jjmr, ubrogepant, rimegepant) during the follow-up period.

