#### 8.3 Variables

#### 8.3.1 Exposure Assessment

The cohorts of erenumab-aooe, other mAbs targeting the CGRP pathway (galcanezumab-gnlm, fremanezumab-vfrm, eptinezumab-jjmr), select SOC migraine preventive medications (anti-epileptics: topiramate, valproic acid, divalproex sodium), and onabotulinumtoxinA initiators will be identified as described in Section 8.2. New use of medications will be based on NDCs or HCPCS codes as captured in the pharmacy tables within the MarketScan® claims database. The list of NDCs and HCPCS codes that will be used for cohort identification is provided in Appendix C.

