### 8.9 Limitations of the Research Methods

### 8.9.1 Internal Validity of Study Design

### 8.9.1.1 Measurement Error/Misclassification

Measurement error may occur when identifying medication cohorts in claims databases because the presence of a claim for a prescription does not necessarily mean that the medication was taken as prescribed. Also, medication given as free samples by a physician will not be observed in claims data. For the current analyses, measurement error may also occur due to the free drug and coupon programs that have been available after launch of CGRP mAbs. Patient assistance programs are often sponsored by pharmaceutical companies to provide drugs at low or no cost to patients who lack prescription drug coverage for a particular medication. Using a different data source (not claims-based), it has been reported that 76% of the first 64439 new users of erenumab-aooe were covered through "discount/coupon" programs (Hines et al, 2019). Analyses using more recent data show that the majority of erenumab-aooe patients  $(\sim 60\%)$  continue to have coverage using this program. Similar programs have been in place for the other mAbs targeting the CGRP pathway. Although this will result in missing claims, it is not expected that this would introduce bias when assessing claims in relation to the outcomes under study. Care should be taken, however, to ensure that results are not interpreted as risk for the outcome in people who have newly started CGRP mAbs, but rather as risks in people who have a first claim in the database.

Patients who receive medical insurance from federal programs, such as Medicaid, are not eligible to receive additional financial assistance (through the Aimovig™ Ally Card) for erenumab-aooe (with the exception of the Safety Net program for Medicare

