### 8.9.4 Limitations Due to Missing Data and/or Incomplete Data

As described in Section 8.9.1.1, because of available free drug coupon programs for mAbs targeting the CGRP pathway, prescriptions for initial use of the medications will be

missing for some patients. Consequently, when using claims data, the CGRP mAb medication cohorts will include incident users of CGRP mAbs, as well as prevalent users of CGRP mAbs.

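### Comparator patients are classed as CGRP-free on claims that miss program-supplied CGRP antibodies, so the no-bias statement is unsupported for erenumab versus anti-epileptics and versus onabotulinumtoxinA

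*Protocol*

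**What the plan says.** **How exposure is found.** Section 8.3.1: "New use of medications will be based on NDCs or HCPCS codes as captured in the pharmacy tables". The CGRP washout uses this information; for onabotulinumtoxinA, Section 8.2.2.2 asks for "no use of any onabotulinumtoxinA or any medication targeting the CGRP pathway in the year prior to the index date", with a matching rule for the anti-epileptic cohort. Per-protocol censoring for switching (Section 8.2.5) uses it too: "For new users of onabotulinumtoxinA, initiation of any medication targeting the CGRP pathway". Section 8.2.2 draws both comparator cohorts from the migraine patients left over once the CGRP antibody cohorts have been formed.

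**What claims miss.** Section 8.2.2: "Use of mAbs targeting the CGRP pathway based on free/discount/coupon programs is not captured in claims data". Section 8.9.1.1 reports, from a source that is not claims-based, that "76% of the first 64439 new users of erenumab-aooe were covered through" discount or coupon programs, and that in later data about 60% "continue to have coverage using this program". It adds that similar programs exist for the other CGRP antibodies.

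**What the protocol concludes.** Section 8.9.1.1 accepts that claims will be missing but says "it is not expected that this would introduce bias when assessing claims in relation to the outcomes under study". The consequence it draws concerns the antibody cohorts only: the earliest prescription record in the database may not mark the start of use. Section 8.9.4 says the same: "the CGRP mAb medication cohorts will include incident users of CGRP mAbs, as well as prevalent users".

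**The concern.** The protocol considers missing claims only as missed starts inside the CGRP antibody cohorts. The same gap works in the other direction. A migraine patient with an anti-epileptic or onabotulinumtoxinA claim who receives erenumab through a program passes the washout, is not censored, and counts as unexposed. This affects contrasts 2 and 3 of Section 8.1 (erenumab versus anti-epileptics, and versus onabotulinumtoxinA).

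The planned safeguards would not reveal it:

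- Negative control outcomes (Section 8.7.2.4) are chosen because treatment cannot cause them, so they do not move when comparator patients take erenumab.
- The Medicaid analysis (Section 8.9.1.1) covers hypertension in the two CGRP antibody cohorts, with no comparison.
- The quantitative bias analysis (Section 8.9.1.4) addresses an unmeasured confounder, smoking.

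At stake is how a null result is read. In a safety study, dilution toward 1 is the unsafe direction, and a risk ratio near 1 could be taken as reassurance although the comparator arm was partly exposed.

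**Working it through.** **Inputs from the protocol.** Section 8.7.2.4 (Decision to Proceed to Comparative Analyses): 15,000 per arm for MI and 3,750 for stroke to detect RR 2.0 with 80% power; background rates 0.15 and 0.60 per 100 person-years. Section 8.5: alpha 0.05, equal arms, about 13,000 onabotulinumtoxinA users.

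**Assumptions.** Two-sided alpha; one year of follow-up per patient, so the rates become risks of 0.0015 and 0.0060. The hidden share h of the comparator arm is not in the documents and is varied.

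**Step 1: reproduce the protocol's sizes.** Schoenfeld events for RR 2.0: 4(1.96 + 0.84)² / (ln 2)², about 66. Patients per arm = 66 / (3 × risk):

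- MI: 66 / 0.0045 = 14,667, against 15,000 stated
- Stroke: 66 / 0.018 = 3,667, against 3,750 stated

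Both agree within 3%. A two-proportion calculation at the stated sizes gives power of 78.3% and 78.6%.

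**Step 2: dilution.** If a share h of the comparator arm carries the erenumab risk, its risk is p0[1 + h(RR − 1)], so

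RR_obs = RR / [1 + h(RR − 1)].

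For a true RR of 2.0 this is 2 / (1 + h). Power compares 2·p0 with p0(1 + h):

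| h | RR_obs | Power, MI, 15,000 per arm | Power, stroke, 3,750 per arm |
|---|---|---|---|
| 0% | 2.00 | 78% | 79% |
| 2% | 1.96 | 76% | 77% |
| 5% | 1.90 | 73% | 74% |
| 10% | 1.82 | 68% | 68% |
| 20% | 1.67 | 57% | 57% |

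With a true RR of 1, the formula gives 1 at any h.

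**Step 3: what h might be.** Let π be the true share of otherwise eligible comparator patients on erenumab (assumed) and m the part of that use that claims miss. After visible users are removed, h = πm / (1 − π + πm). With m = 0.60 to 0.76:

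- π = 2%: h = 1.2% to 1.5%
- π = 5%: h = 3.1% to 3.8%
- π = 10%: h = 6.3% to 7.8%
- π = 20%: h = 13.0% to 16.0%

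A true RR of 2.0 would then read from about 1.98 down to 1.72. Because m is set at the program-coverage figures, these values lean high.

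**Step 4: the correction.** Inverting step 2:

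RR_corrected = RR_obs(1 − h) / (1 − h·RR_obs), valid for h·RR_obs < 1.

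Check: 1.818 × 0.9 / (1 − 0.1818) = 2.00. An RR_obs of 1 returns 1 for every h, so correcting the point estimate alone says nothing about a null result. The limits do move: an upper limit of 2.0 becomes 1.8 / 0.8 = 2.25 at h = 10% and 1.6 / 0.6 = 2.67 at h = 20%.

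**The case against.** The protocol does not hide the coupon gap. Sections 8.2.2, 8.9.1.1, 8.9.2 and 8.9.4 all mention it, and the modeling assumptions in Section 8.7.2.4 list absence of exposure misclassification as a condition. That stands as disclosure. But the discussion deferred from that list never reaches the comparator arms, and Section 8.9.1.1 makes a positive statement that no bias is expected.

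A reader might infer that 60% to 76% of erenumab users never have a claim. The documents do not say so. The figures are program coverage, and Section 8.9.4 says initial prescriptions are missing for some patients, who later appear as prevalent users. The figures are nearer an upper bound on users who never have a claim.

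A reader might also infer that h follows from these figures and the comparator patients with a visible CGRP claim, scaled by the odds of program coverage. It does not. The coverage figures describe erenumab users; visible claims would cover any CGRP drug, including gepants; and patient counts are not person-time. Section 8.2.2 also notes that guidelines place erenumab after two standard preventives. This argues against assuming heavy hidden use among anti-epileptic starters, though it does not exclude it.

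The direction is conditional too. It needs a true effect, hidden use that overlaps follow-up (or an effect that persists), and hidden users whose baseline risk is otherwise typical of the arm. Finally, at about 13,000 patients the onabotulinumtoxinA cohort is projected below the 15,000 required for MI, so that comparison may not be run.

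**Conclusion.** The point holds in a limited form. The protocol's own statements make undetected CGRP antibody use in the two comparator arms plausible, and its expectation of no bias is unsupported for contrasts 2 and 3. The documents do not establish that the arms are contaminated to any particular degree, nor that the reported risk ratios will be biased.

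Under the conditions above, dilution is modest for small h (2.0 reads 1.96 at 2%) and material for larger h (1.67 at 20%, with MI power down from 78% to 57%). These figures rest on assumed h, one year of follow-up, two-sided alpha, and hidden users carrying the erenumab risk. The comparisons most likely to be affected are stroke in both contrasts and MI against anti-epileptics. An unknown hidden share calls for a bias analysis rather than a statement that no bias is expected.

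**What to change.** 1. **Section 8.9.1.1.** For contrasts 2 and 3, replace the no-bias sentence with a statement that undetected program-supplied CGRP antibody use in the comparator arms may bias a non-null risk ratio toward 1.
2. **Section 8.9.1.4.** Add an exposure-misclassification bias analysis using the step 4 correction, over a prespecified, openly assumed range of h (for example 0% to 20%), where h·RR_obs < 1. Apply it to the point estimate and both 95% confidence limits.
3. **Reporting.** Show the result beside each risk ratio in contrasts 2 and 3, so that a null finding is read with its corrected upper limit. Do not derive h from the program-coverage share. In the intention-to-treat analysis, visible switching also stays in the comparator arm by design, so say there that the table addresses hidden use only.

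The cost is some wording, one extra table, and a slightly less reassuring conclusion. The change should be made before comparative results are seen.

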#### 8.2.3 Matching

Matching will not be undertaken in this study.

#### 8.2.4 Baseline Period

The index date for all medication cohorts is the earliest prescription claim date for a given medication occurring during the study period that satisfies the inclusion/exclusion criteria. The 365 days of continuous enrollment (ie, complete medical and pharmacy coverage) prior to and including the index date will be the baseline period.

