### 8.2.2.1 Inclusion Criteria

Patients must meet the following inclusion criteria:

- 1. 18-64 years of age on the index date.
- 2. One year of continuous enrollment (ie, complete medical and pharmacy coverage) prior to and including the index date, which defines the baseline period.
- 3. A diagnosis of migraine during the baseline period, based on one of the following criteria:
  - a) ≥1 inpatient claim with a diagnosis of migraine (ICD-10-CM) diagnosis code of G43.xxx).
  - b) ≥1 outpatient evaluation and management claim with a diagnosis of migraine and a specialty code of 260 (neurologist).
  - c)  $\geq 1$  claim for emergency room visit with a diagnosis of migraine.
  - d) ≥1 outpatient evaluation and management claim with a diagnosis of migraine PLUS ≥1 pharmacy fill for a migraine-specific triptan or an ergotamine class medication within 365 days of each other
  - e) ≥2 outpatient evaluation and management claims with a diagnosis of migraine between 7 and 365 days apart.
  - f) ≥2 pharmacy fills for migraine-specific triptans or ergotamine class medications between 7 and 365 days apart.

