### 8.3.2 Outcome Assessment

The outcomes of interest are hypertension, acute MI, and stroke, which will be identified within the MarketScan® claims database using ICD-10-CM diagnosis codes. The following algorithms will be used for each of the outcomes:

- Hypertension occurrence of one inpatient (IP) diagnosis, one emergency room (ER) diagnosis, or one outpatient (OP) diagnosis during the follow-up period.
- (2) Acute MI occurrence of one diagnosis in the IP setting during the follow-up period.
- (3) Stroke, including both ischemic stroke and hemorrhagic stroke occurrence of one diagnosis in the IP setting during the follow-up period.

All outcomes will be assessed separately starting from the index date through the end of follow-up as described in Section 8.2.5. Only the first (incident) event for each outcome will be included in the analysis. The ICD-10-CM diagnosis codes for hypertension acute MI, and stroke are provided in Appendix C. The validation studies supporting the algorithms and ICD-10-CM diagnosis codes for the outcomes evaluated in this study are

provided in Section 8.3.4. The negative control outcomes that will be used to evaluate exchangeability between study cohorts for the comparative analyses are described in Section 8.7.2.4.

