160.6	ICD-10-CM Diagnosis	Nontraumatic subarachnoid hemorrhage from other intracranial arteries	1 IP
160.7	ICD-10-CM Diagnosis	Nontraumatic subarachnoid hemorrhage from unspecified intracranial artery	1 IP
160.8	ICD-10-CM Diagnosis	Other nontraumatic subarachnoid hemorrhage	1 IP

Code	Code type	Code description	Setting (Any diagnosis position)
160.9	ICD-10-CM Diagnosis	Nontraumatic subarachnoid hemorrhage, unspecified	1 IP
l61	ICD-10-CM Diagnosis	Nontraumatic intracerebral hemorrhage	1 IP
l61.0	ICD-10-CM Diagnosis	Nontraumatic intracerebral hemorrhage in hemisphere, subcortical	1 IP
l61.1	ICD-10-CM Diagnosis	Nontraumatic intracerebral hemorrhage in hemisphere, cortical	1 IP
l61.2	ICD-10-CM Diagnosis	Nontraumatic intracerebral hemorrhage in hemisphere, unspecified	1 IP
161.3	ICD-10-CM Diagnosis	Nontraumatic intracerebral hemorrhage in brain stem	1 IP
l61.4	ICD-10-CM Diagnosis	Nontraumatic intracerebral hemorrhage in cerebellum	1 IP
l61.5	ICD-10-CM Diagnosis	Nontraumatic intracerebral hemorrhage, intraventricular	1 IP
161.6	ICD-10-CM Diagnosis	Nontraumatic intracerebral hemorrhage, multiple localized	1 IP
161.8	ICD-10-CM Diagnosis	Other nontraumatic intracerebral hemorrhage	1 IP
l61.9	ICD-10-CM Diagnosis	Nontraumatic intracerebral hemorrhage, unspecified	1 IP

	1	-		
Characteristic	Treatment Model	Censoring Model	Numerical (N) or categorical (C)	Covariate assessment period*
Demographics	Index Date			
Age (years), 18-24, 25-34, 35-44, 45-54, 55-64	Х	X	С	
Gender (male, female)				
Geographical region (eg, Midwest, Northeast, South, West)	Х	х	С	
Select Migraine Diagnoses				Baseline period
Chronic migraine (without aura)	Х	X	С	
Migraine with aura	Х	Х	С	
Acute Migraine Medications				Baseline period
Triptans	Х	Х	С	
Ergotamines	Х	Х	С	
Nonsteroidal anti- inflammatory drugs (NSAIDs)	Х	X	С	
Opioids	Х	Х	С	
Non-opioid, non-NSAID analgesics	Х	Х	С	
Gepants	Х	Х	С	
Other acute migraine-specific treatments	Х	X	С	
Non-CGRP Mediated Migraine	Preventives			Baseline period
Any MPT	Х	Х	С	
Select anti-depressants	Х	Х	С	
Select anti-epileptics	Х	Х	С	
Botulinum toxins	Х	Х	С	
Other migraine preventive agents	Х	X	С	

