# Appendix D: *A Priori* List of Covariates to be Included in the Treatment and Censoring Modelsa

Footnotes defined on last page of table

Page 1 of 4

Characteristic	Treatment Model	Censoring Model	Numerical (N) or categorical (C)	Covariate assessment period*
Healthcare Utilization	Baseline period, Follow-up			
Ambulatory visits	Х	Х	N	
Emergency room visits	Х	Х	N	
Inpatient hospital visits	Х	Х	N	
Pneumococcal vaccination		Х	С	
Influenza vaccination		Х	С	
Herpes zoster vaccination		Х	С	
Eye exam		Х	С	
Screening colonoscopy		Х	С	
Screening PSA test		Х	С	
Screening fecal occult blood test		Х	С	
Screening mammogram		Х	С	
Oxygen equipment use		Х	С	
Home hospital bed		Х	С	
Mobility aids		Х	С	
Mechanical ventilation		Х	С	
Ambulance / life support		Х	С	
Rehabilitation services		Х	С	
Overall Medication Utilization	Baseline period, Follow- up			
Generic medications dispensed	X	Х	N	
Unique drug classes dispensed	Х	Х	N	

Footnotes defined on last page of table

Page 2 of 4

Characteristic	Treatment Model	Censoring Model	Numerical (N) or categorical (C)	Covariate assessment period*
Other Medications				Baseline Period
Contraceptives	Х	Х	С	
Anti-hypertensives	Х	Х	С	
Anti-coagulants	Х	Х	С	
Anti-platelets	Х	Х	С	
Lipid-lowering agents	Х	Х	С	
Anti-diabetics	Х	Х	С	
Cardiac glycosides	Х	Х	С	
Calcium gluconate	Х	Х	С	
Fludrocortisone/ Midodrine	Х	Х	С	
Weight loss prescriptions	Х	Х	С	
Fludrocortisone/ Midodrine	Х	Х	С	
Hyperpolarization-activated cyclic nucleotide-gated channel blocker	Х	X	С	
Comorbidities	I	1	1	Baseline Period
Diabetes mellitus	Х	Х	С	
Hypercholesterolemia	Х	Х	С	
Hypertension	Х	Х	С	
Liver disease / Cirrhosis	Х	Х	С	
Depression	Х	Х	С	
Chronic Obstructive Pulmonary Disease (COPD)	Х	X	С	
Renal Disease	Х	Х	С	
Cardiac arrhythmia	Х	Х	С	
Asthma	Х	Х	С	
Human immunodeficiency virus (HIV)	Х	Х	С	
Lupus	Х	Х	С	
Epilepsy/Seizure/Convulsions	Х	Х	С	
Anxiety	Х	Х	С	

Footnotes defined on last page of table

Page 3 of 4

Characteristic	Treatment Model	Censoring Model	Numerical (N) or categorical (C)	Covariate assessment period*
Comorbidities (continued)			Baseline Period	
Depression	Х	Х	С	
Peripheral Artery Disease	Х	Х	С	
Venous thromboembolism	Х	Х	С	
Critical limb ischemia	Х	Х	С	
Myocardial Ischemia	Х	Х	С	
Congestive heart failure	Х	Х	С	
Acute myocardial infarction	Х	Х	С	
Unstable angina	Х	Х	С	
Prinzmetal angina	Х	Х	С	
Other and unspecified angina pectoris	Х	Х	С	
Acute atrial fibrillation	Х	Х	С	
Paroxysmal atrial fibrillation	Х	Х	С	

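### Baseline includes the index date, so as written the comparator's own index drug sets propensity-score covariates to 1 in two of the three contrasts

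*Protocol*

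**What the plan says.** **Baseline window.** Protocol 8.2.4 sets the 365 enrolment days "prior to and including the index date will be the baseline period", and inclusion criterion 2 in 8.2.2.1 repeats this ("prior to and including the index date, which defines the baseline period"). Section 8.2.4 also makes the index date the date of the earliest qualifying claim for the cohort drug.

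**Covariates.** Section 8.7.2.4 names Appendix D as the list for the propensity score. Under the block "Non-CGRP Mediated Migraine" preventives, Appendix D marks *Any MPT*, *Select anti-epileptics* and *Botulinum toxins* for both the treatment and the censoring model, assessed over the baseline period. Table 1 itemises the anti-epileptic class to include topiramate, valproic acid and divalproex sodium, and the toxin class to include onabotulinumtoxinA. These are the index drugs of two comparator cohorts.

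**Washout.** Section 8.2.2.2 requires, for the onabotulinumtoxinA cohort, "no use of any onabotulinumtoxinA or any medication targeting the CGRP pathway in the year prior to the index date", with a parallel rule for the three anti-epileptics.

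**Criteria.** Section 8.7.2.4 treats an absolute standardized difference above 0.1 as potential imbalance and lists positivity among the modelling assumptions.

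**Outcome timing.** Section 8.3.2 states: "All outcomes will be assessed separately starting from the index date through the end of follow-up as described in Section 8.2.5". Section 8.2.5 states: "Follow-up begins the day after the index date".

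**The concern.** The claim that places a patient in a comparator cohort falls on the index date, and the index date lies inside the covariate window. Unless the claim is excluded, the treatment becomes its own covariate. An erenumab claim sets none of the non-CGRP preventive flags, so the effect is one-sided.

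Balance and propensity-score overlap feed the decision on whether the acute MI and stroke comparisons go ahead. Two of the three contrasts could be judged non-comparable, or lose many erenumab users to trimming, because of how a window is defined rather than because the patients differ. If the problem is repaired during the iterative process that 8.7.2.4 allows, an input to that decision is changed after the data have been seen.

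**Working it through.** The plan states no figure that depends on this window, so there is none to reproduce.

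**Inputs**
- Comparator flag prevalence: 1, from 8.2.4, Table 1 and Appendix D read literally.
- Erenumab flag prevalence p: not given. Assumed 20%, 40%, 60%. It may differ by flag. The remark in 8.2.2 that guidelines ask for two earlier preventives suggests it is highest for any MPT.
- Projected cohorts (8.5): about 20,000 erenumab and 13,000 onabotulinumtoxinA.
- Limits (8.7.2.4): standardized difference 0.1; 15,000 per arm for acute MI and 3,750 for stroke.

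**Step 1: unweighted difference.** The comparator variance is 0, so SMD = (1−p)/√(p(1−p)/2) = √(2(1−p)/p). To reach 0.1 requires 2(1−p)/p ≤ 0.01, so p ≥ 2/2.01 = 99.5%.

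**Step 2: after weighting by this flag alone (contrast 3).** All 13,000 comparators are flagged. Weighted erenumab prevalence is (20,000p + 13,000)/33,000. The gap to 1 is therefore (1−p) × 20/33, and with the unweighted SD as denominator the SMD is 20/33 of Step 1. The weight of a flagged erenumab user is (20,000p + 13,000)/(20,000p).

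| p | SMD unweighted | SMD weighted | Weight, flagged erenumab | Erenumab left if all unflagged are trimmed |
|---|---|---|---|---|
| 20% | 2.83 | 1.71 | 17,000/4,000 = 4.25 | 4,000 |
| 40% | 1.73 | 1.05 | 21,000/8,000 = 2.63 | 8,000 |
| 60% | 1.15 | 0.70 | 25,000/12,000 = 2.08 | 12,000 |

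Among unflagged patients the probability of erenumab is exactly 1, so positivity fails there. Trimming them leaves 20,000p. That is below 15,000 unless p ≥ 75%, and below 3,750 unless p ≥ 18.75%. In contrast 3 the projected 13,000 comparators already fall short of 15,000, so the MI consequence bears on contrast 2.

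**Step 3: does ending the window the day before index suffice?** The washout then makes prior onabotulinumtoxinA 0 for every patient in that cohort. Ignoring other toxins, SMD = √(2p/(1−p)) = 0.71, 1.15 and 1.73 at 20%, 40% and 60%. Weighted by the same 20/33 factor, this is 0.43, 0.70 and 1.05. All exceed 0.1, and at 60% the difference is larger than before. For the anti-epileptic flag only the three washed-out drugs are forced to 0, so the remainder is smaller and cannot be sized from the protocol.

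**Step 4: outcome timing.** Section 8.3.2 starts outcomes on the index date but defers to 8.2.5 in the same sentence. Section 8.2.5 starts follow-up one day later in both analyses. The index day belongs to baseline in 8.2.4 and cannot also be outcome time.

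**The case against.** The best defence is that the sponsor did not mean this. The eligibility summary in the Abstract bars any CGRP-pathway drug during baseline. If the index claim counted, both CGRP cohorts would be empty, while 8.2.2.2 words the washout as the year before the index date. In 8.2.4 the word *including* sits in a sentence about enrolment. Appendix D's assessment-period column carries an asterisk whose footnote does not appear in the available text, and it may define the window. A flag at 100% would also stand out in the baseline tables. This makes an unintended slip likely. It does not change the stated rule: two sections include the index date, and no visible sentence exempts the index claim from the covariates.

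A reader might infer more than the protocol supports:
- *Exploding weights.* On this flag alone they are about 2 to 4; the failure is one of positivity.
- *Distorted drug counts.* The "Generic medications dispensed" count rises by one in every cohort, so no differential effect is shown.
- *Double-counted new-onset hypertension.* Section 8.3.4 removes anyone with baseline hypertension from that analysis, so an index-day code cannot also be a new-onset event.
- *A large visit-count bias.* One extra index-day visit among onabotulinumtoxinA users would shift the SMD by 1/SD (0.20, 0.10 or 0.05 at assumed SDs of 5, 10 or 20). The protocol does not say that such an encounter counts, and 8.3.1 refers to pharmacy tables. This is an inference of unknown size.

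**Conclusion.** The point holds for contrasts 2 and 3 and not for contrast 1, where the index drug is not an Appendix D covariate. As written, the covariate window puts the comparator's index drug into the propensity-score model. Positivity fails for unflagged erenumab users, and weighting cannot reach 0.1: the unweighted differences are 2.8, 1.7 and 1.2 at p = 20%, 40% and 60%. The direction rests on the text alone. The size rests on the assumed p and on *Select anti-epileptics* and *Any MPT* following Table 1, since Appendix D does not itemise them. It should be corrected before comparability is assessed.

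It would be wrong to conclude that moving one date boundary solves it, because the washout then creates the opposite imbalance. The conflict between 8.3.2 and 8.2.5 is a wording conflict to reconcile, not evidence of miscounted events.

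**What to change.** 1. In 8.2.4, Table 1 and Appendix D, assess medication and utilization covariates on days before the index date, excluding the index claim. Diagnoses may still run through the index date.
2. For contrasts 2 and 3, either remove the cohort-defining drug from the class and any-MPT covariates, or restrict the erenumab arm to patients without prior use of it. Removal keeps every patient but leaves that prior use unadjusted. Restriction keeps 20,000(1−p) erenumab users: 16,000, 12,000 or 8,000 at p = 20%, 40% or 60%. That meets 15,000 only if p ≤ 25% and 3,750 if p ≤ 81.25%.
3. In 8.7.2.5.3, bar the index drug and its procedure code from the high-dimensional propensity-score candidates.
4. Align 8.3.2 with 8.2.5 so that index-day codes count as baseline history only.

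The cost is protocol wording and covariate programming, plus the lost erenumab users if restriction is chosen.
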